8.4.3 Criteria for Treatment Interruption and Dose Reductions

All toxicities that occur during the study will be actively managed following the standard of care unless otherwise specified in the protocol. Patients experiencing AEs attributed to modakafusp alfa may continue study treatment with the same dose, may have modakafusp alfa treatment held,

dose reduced, discontinued, or may be permanently discontinued from the study. Patients who have study drug held because of treatment-related or possibly related AEs may resume study drug treatment after resolution of the AE at the same dose level or at a reduced dose, depending on the nature and severity of the AE and whether it is the first occurrence or is recurrent unless otherwise specified in the protocol.

Table 8.a provides general dose modification recommendations for Parts 1 and 2, Table 8.b and Table 8.c provide dose modification guidelines for Part 3, and Table 8.e provides dose modification recommendations for bleeding TEAEs to mitigate the risk of fatal hemorrhagic events. When the dose of modakafusp alfa is withheld on the basis of these criteria, clinical and laboratory re-evaluation should be repeated at least weekly or more frequently, depending on the nature of the toxicity observed, until the toxicity resolves to Grade ≤1 or baseline. If there are transient laboratory abnormalities that, based on investigator assessment, are not clinically significant or drug related, continuation of therapy without dose modification is permissible upon discussion with the sponsor. See details for managing specific AEs in Section 8.7.1.

When a dose reduction occurs, the modakafusp alfa dose will be reduced to the next lower dose that has been established as a safe dose during dose escalation. For Parts 1 and 2, if the initial dose adjustment does not provide sufficient relief, the dose of modakafusp alfa can be further reduced if the treating physician considers that the patient is receiving benefit. In general, after a dose is reduced, it should not be re-escalated even if there is minimal or no toxicity with the reduced dose. However, if further evaluation reveals that the AE that led to the dose reduction was not study drug related, the dose may be re-escalated to the original dose level. For Parts 1 and 2, up to 2 dose level reductions of modakafusp alfa because of AE are generally recommended.

The dose of modakafusp alfa will not be reduced for an individual patient during Cycle 1 unless a DLT has been declared and it is still possible for the patient to receive treatment within the remaining dosing period scheduled. In this case, the patient can complete Cycle 1 at a reduced dose level.

8.4.3.1 Parts 1 and 2

Table 8.a Parts 1 and 2 Dose Modification Recommendations for Modakafusp Alfa Toxicities

This table does not include guidance for management of bleeding TEAEs and IRRs. Refer to Table 8.e for the management of bleeding TEAEs and Table 8.g and Table 8.h for the management of IRRs.

Criteria	Action
Grade 1 AEs	No dose reductions or interruptions.
Grade 2 AEs	Treat according to local practice. Whether to hold treatment or to continue it at the same or a reduced dose (Table 8.d) is at the discretion of the investigator.
	Patients experiencing Grade 2 AEs considered related to study treatment that are not easily managed or corrected and are not tolerable to the patient, or AEs that are not acceptable in the investigator's judgment, should have study treatment interrupted until the AE resolves to Grade ≤1 or baseline and then restarted at the same dose or, depending on the toxicity, at the previous safe dose level or below.
Grade 3, Grade 4 (not life-threatening), and Grade 4 asymptomatic laboratory AEs	Hold modakafusp alfa until resolution to Grade ≤1 or baseline, and then resume treatment at either the same dose or a reduced dose level at the discretion of the investigator.
Grade 4 (life-threatening) AEs	Consider permanently withdrawing the patient from the study, except when the investigator determines that the patient is receiving clinical benefit and has discussed this with the sponsor. Treatment may be restarted at a reduced dose level or below when toxicity recovers to Grade ≤1 or baseline.
AEs of all grades	If treatment has been held for >14 consecutive days without resolution of the toxicity (to baseline or Grade ≤1), consider permanently discontinuing study treatment unless there is clinical benefit for the patient as assessed by the investigator and with sponsor's approval. Treatment can be resumed at a reduced dose level after resolution of AEs to Grade ≤1 or baseline.

AE: adverse event; IRR: infusion-related reaction; TEAE: treatment-emergent adverse event. This table does not include guidance for the management of bleeding TEAEs, which is found in Table 8.e or for the management of IRRs, which is found in Table 8.g, Table 8.h, Section 8.7.1.1.1, and Section 8.7.1.1.2.

8.4.3.2 Part 3

Part 3 dose modification recommendations for hematologic and nonhematologic toxicities are detailed in Table 8.b and Table 8.c, respectively, and Part 3 dose reduction levels are found in Table 8.d.

Table 8.b Part 3 Dose Modification Recommendations for Modakafusp Alfa Hematological Toxicities

This table does not include guidance for management of bleeding TEAEs and IRRs. Refer to Table 8.e for the management of bleeding TEAEs and Table 8.g and Table 8.h for the management of IRRs.

Criteria	Action
Grade 1 and 2 AEs	No dose reductions or interruptions.
Grade 3 and 4 AEs	Hold modakafusp alfa next infusion until resolution to Grade ≤2 then resume treatment.
	Consider growth factors and/or transfusion according to local practice.
	If the next cycle of modakafusp alfa is delayed for >28 days, study treatment should be discontinued unless the investigator considers that the patient will receive benefit continuing in the study.
	Dose reduction can be considered.

AE: adverse event; IRR: infusion-related reaction; TEAE: treatment-emergent adverse event. This table does not include guidance for the management of bleeding TEAEs, which is found in Table 8.e or for the management of IRRs, which is found in Table 8.g, Table 8.h, Section 8.7.1.1.1, and Section 8.7.1.1.2.

Table 8.c Part 3 Dose Modification Recommendations for Modakafusp Alfa Non Hematological Toxicities

This table does not include guidance for management of bleeding TEAEs and IRRs. Refer to Table 8.e for the management of bleeding TEAEs and Table 8.g and Table 8.h for the management of IRRs.

Criteria	Action
Grade 1 and 2 AEs	No dose reductions or interruptions. Treat according to local practice.
Grade 3 AEs and Asymptomatic Grade 4 laboratory AEs	Hold modakafusp alfa next infusion until resolution to Grade ≤1 or baseline, and then resume treatment.
	1st occurrence: Resume treatment at either the same dose or reduced dose at the discretion of the investigator.
	Subsequent occurrence: Reduce modakafusp alfa by 1 dose level.
	If treatment has been held for >28 consecutive days without resolution of the toxicity (to baseline or Grade ≤1), consider permanently discontinuing study treatment unless there is clinical benefit for the patient as assessed by the investigator and with sponsor's approval.
Grade 4 AEs (except asymptomatic Grade 4 laboratory AEs)	Permanently withdraw the patient from the study, except when the investigator determines that the patient is receiving clinical benefit and has discussed this with the sponsor.

AE: adverse event; IRR: infusion-related reaction; TEAE: treatment-emergent adverse event. This table does not include guidance for the management of bleeding TEAEs, which is found in Table 8.e or for the management of IRRs, which is found in Table 8.g, Table 8.h, Section 8.7.1.1.1, and Section 8.7.1.1.2.

Potential dose modifications in Part 3 are to be discussed with the sponsor before implementation.

Table 8.d Part 3 Dose Reduction Levels

	120 mg	240 mg
1st dose level reduction	80 mg	160 mg
2nd dose level reduction	Discontinue treatment	120 mg
3rd dose level reduction	NA	Discontinue treatment

NA: not applicable.

8.4.3.3 Parts 1. 2. and 3

Table 8.e provides dose modification recommendations for bleeding TEAEs in Parts 1, 2, and 3 to mitigate the risk of fatal hemorrhagic events.

Table 8.e Parts 1, 2, and 3 Dose Modification Recommendations for Modakafusp Alfa Bleeding TEAEs

This table does not include guidance for management of IRRs. Refer to Table 8.g and Table 8.h for the management of IRRs.

Criteria	Action
Grade 1 and 2	No dose reductions or interruptions. Treat according to local practice.
Grade 3 without associated Grade 4 thrombocytopenia	Hold next infusion of modakafusp alfa until resolution to Grade ≤1 or baseline, and then resume treatment. Subsequent occurrence: Discontinue modakafusp alfa.
Grade 3 with associated Grade 4 thrombocytopenia	Discontinue modakafusp alfa.
Grade 4	Discontinue modakafusp alfa.

IRR: infusion-related reaction; TEAE: treatment-emergent adverse event.

This table does not include guidance for the management of IRRs, which is found in Table 8.g, Table 8.h, Section 8.7.1.1.1, and Section 8.7.1.1.2.

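### Table 8.a, for weight-dosed Parts 1 and 2, points to the Part 3 fixed-dose reduction table, which disagrees with the Section 8.4.3 text on the size and number of reductions

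*Protocol*

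**What the plan says.** Four places in the Protocol bear on this.

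- **Section 8.4.3.1.** The table is headed "Table 8.a Parts 1 and 2 Dose Modification Recommendations for Modakafusp Alfa Toxicities". Its Grade 2 row contains the pointer: "Whether to hold treatment or to continue it at the same or a reduced dose (Table 8.d) is at the discretion of the investigator". The Grade 3, Grade 4 and all-grades rows mention a reduced level but cite no table for it.
- **Section 8.4.3.2.** The target of the pointer is "Table 8.d Part 3 Dose Reduction Levels", and the text introducing it agrees: "Part 3 dose reduction levels are found in Table 8.d". It has two columns, 120 mg and 240 mg. Its first two rows read "1st dose level reduction 80 mg 160 mg" and "2nd dose level reduction Discontinue treatment 120 mg". The third row stops treatment in the 240 mg column.
- **Section 8.4.3, body text.** When a reduction is made, "the modakafusp alfa dose will be reduced to the next lower dose that has been established as a safe dose during dose escalation". The same section generally recommends no more than two reductions for adverse events in Parts 1 and 2.
- **Section 8.1.** Doses in Parts 1 and 2 are set from screening weight; Part 3 uses the fixed doses. SAP Section 7.7 follows the same split, with mg/kg for Parts 1 and 2 and mg for Part 3.

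The documents contain no table of mg/kg reduction levels for Parts 1 and 2.

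**The concern.** An investigator treating a Part 1 or Part 2 patient with a Grade 2 event is sent to a table written for another part of the study and another dosing basis. That table does not match the body text of the same section, and nothing says which of the two prevails.

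What is at stake is consistent management of toxicity. Section 8.4.3 is operative safety text; Amendment 10 v2 revised it as part of an urgent safety measure. The requirement to discuss dose modifications with the sponsor beforehand is stated in Section 8.4.3.2 for Part 3. For the Grade 2 row of Table 8.a the choice rests with the investigator, and Section 8.4 says only that clarification is available from the sponsor clinician. A site could therefore act on the pointer without a prior check.

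**Working it through.** **1. The protocol's own conversion.** Section 2.0 and Section 4.6.2.1 turn the two mg/kg doses into fixed doses at a median weight of about 80 kg:

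- 1.5 mg/kg × 80 kg = 120 mg
- 3 mg/kg × 80 kg = 240 mg

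Both stated figures are reproduced exactly.

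**2. Table 8.d against the Section 8.4.3 text.**

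| Feature | Section 8.4.3 text (Parts 1 and 2) | Table 8.d |
|---|---|---|
| Unit | Compatible with mg/kg | Flat mg only |
| Level after one reduction | Nearest lower level found safe in escalation | 80 mg (from 120 mg) or 160 mg (from 240 mg) |
| Reductions before stopping | Up to 2, as a general recommendation | 1 in the 120 mg column, 2 in the 240 mg column |
| Dose levels covered | Any level with a lower safe one | 120 mg and 240 mg only |

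An example of the difference in level, at 80 kg and 1.5 mg/kg (120 mg): Table 8.d gives 80 mg. The next lower level on the planned ladder in Section 2.0 is 0.75 mg/kg, and 0.75 × 80 = 60 mg. The example uses the planned ladder. Section 4.6.2 reports 10 levels explored, so an intermediate level may exist and the second figure could differ.

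**3. A hypothetical reading of the columns.** Suppose a site treats 1.5 mg/kg as the 120 mg column and 3 mg/kg as the 240 mg column. The break-even weight is the flat dose divided by the current mg/kg dose:

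- First reduction from 1.5 mg/kg: 80 / 1.5 = 53.3 kg
- First reduction from 3 mg/kg: 160 / 3 = 53.3 kg

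Below 53.3 kg the tabulated step is higher than the dose being given:

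| Weight (kg) | 1.5 mg/kg (mg) | Table step (mg) | 3 mg/kg (mg) | Table step (mg) | Step / current dose |
|---|---|---|---|---|---|
| 40 | 60 | 80 | 120 | 160 | 1.33 |
| 45 | 67.5 | 80 | 135 | 160 | 1.19 |
| 50 | 75 | 80 | 150 | 160 | 1.07 |
| 55 | 82.5 | 80 | 165 | 160 | 0.97 |
| 60 | 90 | 80 | 180 | 160 | 0.89 |
| 80 | 120 | 80 | 240 | 160 | 0.67 |

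The ratio is the same for both doses because 80/1.5 = 160/3.

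**The case against.** The strongest reply is that this is a stray cross-reference that would mislead few readers. Table 8.d carries a Part 3 label and has no mg/kg column. The 80 kg conversion is used only to set the Part 3 starting doses; no passage extends it to reductions in Parts 1 and 2. The body text of Section 8.4.3 is compatible with mg/kg dosing and always points downward. The same Grade 2 cell also speaks of restarting at a previous safe level or lower. Only one discretionary sentence cites the table, and the rows for more severe events do not. Part 1 escalation is over, and Section 4.6.2 already reports a response rate for the 1.5 mg/kg Part 2 cohort of 25.

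Most of this stands, and it rules out two stronger inferences.

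- A reader might infer that the protocol directs a higher dose, in the name of a reduction, for lighter patients. It does not. That result needs a mapping the protocol never makes for these patients, and it requires setting aside the Section 8.4.3 text.
- A reader might infer that dose-intensity summaries for Parts 1 and 2 are compromised. SAP Section 7.7 fixes the unit as mg/kg for those parts and leaves the algorithm to the dataset specifications. Nothing shows that the pointer reaches those summaries.

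The reply does not remove the contradiction. The pointer is in current text, the table and the body text differ on level and number of steps, and no order of precedence is given. Section 6.3.1 lets Parts 1 and 2 patients with benefit continue beyond one year with sponsor approval, so the text may still apply to someone. The documents do not say how many remain on treatment.

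**Conclusion.** The point holds as an internal inconsistency in operative toxicity-management text. That finding rests on the wording alone.

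The 53.3 kg threshold is correct arithmetic but conditional. It assumes that the columns are read through the 80 kg conversion and that the body text is not followed. The documents give only a median weight of about 80 kg, so the number of Parts 1 and 2 patients below the threshold cannot be stated. It illustrates why the pointer is a poor fit and is not an estimate of harm.

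The point has no bearing on sample size, alpha, power or any planned analysis. It should be corrected, as a modest item.

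**What to change.** Reconcile three passages: the pointer in the Grade 2 row of Table 8.a, the scope and content of Table 8.d, and the reduction text in Section 8.4.3. State in one place how reductions are defined for weight-dosed patients, including the number of steps and the mg/kg levels that have no column in Table 8.d, and have the other passages refer to it. Which passage governs, and at what levels, is for the sponsor's clinical team; no dose or rule is proposed here.

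The cost is a cross-reference and wording edit, which can be carried in the next amendment or a clarification to sites. No analysis needs to change.

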8.7.1.2 Handling of Low Platelet Counts

Treatment decisions will be based on patient platelet counts assessed before any transfusion. Low platelet counts (Grade 4) should cause scheduled infusions to be postponed or to be

permanently discontinued. Please see Table 8.e for dose modifications for bleeding TEAEs for Parts 1, 2, and 3. If at any time the platelet count is less than $10 \times 10^9 / L$ the patient should be withdrawn from modakafusp alfa treatment unless clinical benefit is observed and the investigator considers that thrombocytopenia can be managed, including with dose modifications. The investigator can consider the usage of corticosteroids, IVIG, or thrombopoietin agonists in selected cases depending on severity, duration, transfusion requirements, and additional risk factors for bleeding and based on the suspected underlying mechanism. Platelet transfusion and daily monitoring of platelet counts are recommended.

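### For Part 3 patients without bleeding whose platelets fall below 10 × 10⁹/L, protocol Table 8.b and Section 8.7.1.2 give different stop-or-resume instructions, and no passage says which prevails

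*Protocol*

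**What the plan says.** Three parts of the protocol bear on a low platelet count in Part 3.

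- **Table 8.b (Section 8.4.3.2), Grade 3 and 4 hematological toxicities.** "Hold modakafusp alfa next infusion until resolution to Grade ≤2 then resume treatment". Treatment stops only if the next cycle slips by more than 28 days, and not even then if the investigator expects benefit. Dose reduction is an option. The table has no platelet threshold for withdrawal. Its stated exclusions are bleeding and infusion reactions: "This table does not include guidance for management of bleeding TEAEs and IRRs. Refer to Table 8.e for the management of bleeding TEAEs".
- **Section 8.7.1.2, low platelet counts.** This section is not limited to any Part. At Grade 4, "Low platelet counts (Grade 4) should cause scheduled infusions to be postponed" or stopped for good. For a count under 10 × 10⁹/L at any point, "the patient should be withdrawn from modakafusp alfa treatment unless clinical benefit is observed" and the investigator also considers the thrombocytopenia manageable, dose changes included.
- **Table 8.e (Section 8.4.3.3).** "Table 8.e provides dose modification recommendations for bleeding TEAEs in Parts 1, 2, and 3". It grades the bleeding event, not the platelet count.

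Section 8.4.3 tells the reader to look in 8.7.1 for the handling of specific events. Its rule on resuming after a hold yields to anything specified elsewhere in the protocol. Section 8.4.3.2 asks for sponsor discussion before a Part 3 dose modification, and Section 8.4.4 asks for discussion with the sponsor or CRO before a discontinuation.

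**The concern.** Both passages apply on their face to the same patient. One makes resumption the default after recovery. The other makes withdrawal the default because the count was reached at all, whether or not it recovered. A site working from the Part 3 dose-modification tables has no prompt to open 8.7.1.2, and a site working from 8.7.1.2 is sent to Table 8.e but not to Table 8.b. At stake is whether a stopping rule on a safety-critical count is applied in the same way across about 100 planned sites.

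**Working it through.** The protocol gives no figure to reproduce here, so the check compares the passages case by case for Part 3.

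| Case | Table 8.b | Section 8.7.1.2 | Other text | Result |
|---|---|---|---|---|
| Grade 3 count, no bleeding | Hold, then resume | Silent | – | No conflict |
| Grade 4 count, at or above 10 × 10⁹/L, no bleeding | Hold, then resume | Postpone or stop for good | – | The hold is one of two permitted actions: discretion, not contradiction |
| Count below 10 × 10⁹/L, no bleeding | Hold, then resume; stop only after a delay of more than 28 days | Withdraw by default, with a two-part exception | 8.4.3 points to 8.7.1 | **Different defaults** |
| Grade 1–2 bleeding with Grade 4 count | Bleeding referred to Table 8.e | Postpone or stop | 8.4.2 bars a new cycle below 50,000/mm³ | Infusion does not go ahead |
| Grade 3 bleeding with Grade 4 count | Bleeding referred to Table 8.e | Refers to Table 8.e | Table 8.e: discontinue | No conflict between the tables |

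**The third case, followed through.** Take a patient whose count is below 10 × 10⁹/L at Cycle 1 Day 15, a scheduled Part 3 hematology visit. By Cycle 2 Day 1 the patient has recovered to Grade 2 or better and meets the 8.4.2 criteria.

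1. Table 8.b: the hold condition has cleared, there is no delay beyond 28 days, and treatment resumes.
2. Section 8.7.1.2: the threshold was crossed, so withdrawal is the default. Recovery alone does not lift it.
3. The exceptions do not bring the two together. The one in Table 8.b looks forward to expected benefit and applies only after the long delay. The one in 8.7.1.2 needs benefit already observed, plus manageability. In Appendix A Table 12 the first on-treatment response assessment is at Cycle 2 Day 1, and Appendix F requires two consecutive assessments for a partial response. On the scheduled assessments no confirmed response can exist at that visit, and 8.7.1.2 does not say what else counts as benefit.

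**Cross-references.** The Table 8.b footnote names Table 8.e, Tables 8.g and 8.h, and Sections 8.7.1.1.1 and 8.7.1.1.2, but not 8.7.1.2. Section 8.7.1.2 does not name Table 8.b. Section 8.4.4, on criteria for discontinuing, omits the 10 × 10⁹/L threshold.

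**How many patients.** Section 4.6.2 reports Grade 4 thrombocytopenia in 17% of earlier patients. If that rate held in Part 3, 0.17 × 118 = 20.06, or about 20 patients per arm, would reach Grade 4. Those below 10 × 10⁹/L are an unstated subset, anywhere from 0 to about 20 per arm.

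**The case against.** The best defence is that the passages can be read together. Table 8.b is a general recommendation for all hematological toxicities, and 8.7.1.2 is the specific rule for one of them. Section 8.4.3 sends the reader to 8.7.1 and lets resumption after a hold give way to other protocol text. Withdrawal under 8.7.1.2 is not absolute, and the site does not decide alone.

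Much of this stands. It makes 8.7.1.2 the more natural reading for someone who has both passages in view, and sponsor discussion should catch some divergence. It does not close the gap. The pointer is general, no sentence ranks the two rules, and discussion with the sponsor supplies a conversation rather than a rule.

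Three stronger readings are tempting, and the documents do not support them.

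- **That Table 8.e is a third conflicting instruction.** Its lowest row, "Grade 1 and 2 No dose reductions or interruptions. Treat according to local practice", looks at odds with postponing for Grade 4 platelets. But it concerns the bleed. Every Part 3 infusion starts a new cycle, and 8.4.2 bars a cycle below 50,000/mm³. Section 8.6.3 also rules out platelet transfusion given only to meet that criterion. The row "Grade 3 with associated Grade 4 thrombocytopenia" falls outside Table 8.b altogether.
- **That the conflict covers severe thrombocytopenia in general.** The table above shows none at Grade 3, and only discretion at Grade 4 with a count of 10 × 10⁹/L or more.
- **That the response rate or the dose choice would shift by a calculable amount.** That would need the share of patients below 10 × 10⁹/L and platelet nadirs by dose, and neither is given. It would also need withdrawn patients to be non-responders, whereas SAP Sections 5.3.4 and 7.8.2.1 count assessments after treatment discontinuation, up to progression or subsequent therapy. Section 4.6.2 adds that toxicities rarely led to discontinuation.

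**Conclusion.** The point holds in a narrow form. For Part 3 thrombocytopenia without bleeding and with platelets below 10 × 10⁹/L, Table 8.b and Section 8.7.1.2 set different defaults, and nothing states which governs. The consequence is that a safety stopping rule may be applied inconsistently in an unknown number of patients. The figure of about 20 per arm is only a loose ceiling and assumes that the earlier 17% Grade 4 rate carries over to both arms. This is an inconsistency of wording, not a fault in the statistical design, and no change in power, response rate or dose selection is claimed. The conclusion rests on the text alone; it does not depend on which rule is clinically preferable.

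**What to change.** Reconcile Table 8.b with Section 8.7.1.2 so that a count below 10 × 10⁹/L leads to one instruction. Either add the case to Table 8.b or put a cross-reference to 8.7.1.2 in its caption and footnote. In both passages, state which prevails, and carry the same wording into 8.4.4. The choice of instruction belongs to the sponsor's clinicians.

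The cost is a few lines of protocol text. No new visits, samples or analyses are needed, because Part 3 hematology is already scheduled. A listing of Part 3 patients with a count below 10 × 10⁹/L and the action taken for each could be drawn from data already collected, and it would show how many patients the inconsistency touched.
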